5.7. Lost to Follow Up or Lapse of Adequate Assessments

If a subject has missed two or more scheduled disease assessments, a censoring date will be required in support of relevant efficacy survival derivations. For example, PFS will be censored at the last adequate disease assessment prior to the lost to follow up window. However, this survival outcome would be considered censored after an extended amount of time without additional assessment (after two have been missed). Based on a protocol specified disease assessment schedule of every other cycle (every 8 weeks, up to 7 days prior to dosing), a lapse window of 112 days would be used to establish a censoring date.

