Tumor imaging and evaluation will be assessed at Screening and during the Treatment and Evaluation Period approximately every 6 weeks after initiation of study drug. Tumor measurement and assignment of response will be determined by local Investigators. For subjects on treatment more than 12 months, the frequency of imaging may be reduced to every 12 weeks. Peripheral blood will be collected to assess immune responses directed against *Lm*, mesothelin, and other tumor-associated antigens. Archived tumor tissue and paired tumor biopsies (collected at Screening and during Cycle 2) will be used to explore the association of PD-L1 expression, mesothelin expression, and TIL characteristics with clinical responses.

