6.4.2.1 Tumor Imaging and Response Assessments

Computed tomography (CT) scans of the chest, abdomen and pelvis will be performed at screening (pre-treatment baseline assessment) within 28 days of first dose of study drug and at approximately 6 week intervals after initiation of study drug using the same assessment technique. If CT scan is contraindicated (e.g. allergy to contrast dye), magnetic resonance imaging (MRI) should be performed. Subjects with previously treated brain metastases must be stable (without evidence of progression by imaging at least 4 weeks prior to the first dose of study drug and neurologic symptoms have returned to baseline), have no evidence of new or enlarging brain metastases. Radiographic tumor evaluation should include CT of all affected sites.

For each scan, tumor measurements should be obtained using RECIST v1.1 and assessment of response determined by the local Investigator. The investigator/local radiology review will also use irRECIST ([Section 11](#)) to assess tumor response and progression, and make treatment decisions. If radiographic disease progression is observed, another scan should be done at least four weeks later to confirm disease progression prior to treatment discontinuation. Subjects discontinued after confirmation of progression will enter the Follow-Up Period. Subjects that discontinue all study drugs and complete the EOT without documented progressive disease (based on RECIST v1.1) will be asked to complete tumor imaging every 6 weeks until documented disease progression or start of another anticancer therapy.

The method of assessment and technique should be consistent throughout the study to enable characterization of each identified and reported lesion.

For subjects on treatment more than 12 months, the frequency of imaging may be reduced to every 12 weeks.

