3. STUDY DESIGN

3.1. Study Design and Population

ADU-CL-14 is an open-label, single-arm, multicenter clinical study in approximately 79 adults with recurrent or metastatic gastric, gastroesophageal junction (GEJ), or esophageal adenocarcinomas who have received one or two prior systemic chemotherapy treatment regimens for advanced disease. Of the approximately 79 evaluable subjects, the study will seek to enroll approximately 50 subjects with gastric/GEJ adenocarcinomas and approximately 29 subjects with esophageal adenocarcinoma to achieve adequate representation of each tumor type.

The study design consists of a 28-day Screening Period, Treatment and Evaluation Period (including a Safety Run-in), and a Follow-up Period. CRS-207 and pembrolizumab will be administered in 3-week cycles. For Cycle 1, pembrolizumab (200 mg) will be administered by IV over 30 minutes on Day 1 and CRS-207 (starting dose 1×10^9 CFU) will be administered IV over 1 hour on Day 2. If the infusions are well tolerated, pembrolizumab and CRS-207 may be administered on the same day (Day 1) for subsequent cycles. After 4 cycles, pembrolizumab will continue to be administered on Day 1 at each treatment cycle (every 3 weeks; Q3W), and CRS-207 will be administered once every 6 weeks (i.e. every other treatment cycle; Q6W).

Treatment cycles will continue for up to 24 months as long as there is adequate safety and potential for clinical benefit. If radiographic disease progression is observed, clinically stable subjects who meet dosing eligibility may continue to receive CRS-207 and pembrolizumab according irRECIST guidelines. Subjects who experience an unacceptable toxicity directly attributable to either pembrolizumab or CRS-207 may continue on study and receive either pembrolizumab or CRS-207 as single agent study treatment with approval by the Medical

Sponsor: Aduro Biotech, Inc.
Protocol Number: ADU-CL-14
Version and Date: Version 1.0, 13Mar2018

Monitor. Alternatively, study drug administration may revert back to consecutive day-dosing regimen as performed in Cycle 1 (Day 1 pembrolizumab and Day 2 CRS-207).

The Treatment and Evaluation Period is defined as the time from Day 1 until discontinuation of both CRS-207 and pembrolizumab, completion of an End-of-Treatment (EOT) Visit, and documented disease progression.

Blood will be collected at EOT to assess clearance of CRS-207 [REDACTED]

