Tumor imaging and evaluation will be assessed at Screening and during the Treatment and Evaluation Period approximately every 6 weeks after initiation of study drug. Tumor measurement and assignment of response will be determined by local Investigators. For subjects on treatment more than 12 months, the frequency of imaging may be reduced to every 12 weeks. Peripheral blood will be collected to assess immune responses directed against *Listeria monocytogenes*, mesothelin, and other tumor-associated antigens. Archived tumor tissue and paired tumor biopsies (collected at Screening and during Cycle 2) will be used to explore the association of PD-L1 expression, mesothelin expression, and TIL characteristics with clinical responses.

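### The SAP's 112-day lapse window for PFS and DOR rests on an 8-week imaging schedule this trial does not have; two 6-week intervals are 84 days, or 91 to 98 with a visit allowance

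*SAP*

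**What the plan says.** SAP 5.7 gives the trigger: "If a subject has missed two or more scheduled disease assessments, a censoring date will be required in support of relevant efficacy survival derivations". It then turns that trigger into a number of days, citing what it calls the protocol's "disease assessment schedule of every other cycle (every 8 weeks, up to 7 days prior to dosing), a lapse window of 112 days".

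The schedule is stated differently everywhere else:

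- Protocol 6.4.2.1 has CT scans "at approximately 6 week intervals after initiation of study drug using the same assessment technique". It keeps a 6-week interval for subjects who stop treatment without progression.
- SAP 3.1 places imaging in the "Treatment and Evaluation Period approximately every 6 weeks after initiation of study drug".
- SAP 3.1 also says "CRS-207 and pembrolizumab will be administered in 3-week cycles", so every other cycle is 6 weeks.
- Protocol 6.1 adds one option: "For subjects on treatment more than 12 months, the frequency of imaging may be reduced to every 12 weeks". SAP 3.1 repeats it.

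SAP 7.2 uses the 5.7 window to decide whether a late progression or death is a PFS event, and applies similar censoring to DOR. SAP section 11 lists the changes to the planned analysis and mentions no change of imaging schedule.

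**The concern.** An 8-week interval for every other cycle would need 4-week cycles. The sentence that sets the window therefore conflicts with the cycle length in the same document and with the protocol it cites.

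The window is the only test that separates a counted late event from a censored one. If it is longer than two real intervals, some events that follow two missed scans are counted, against the SAP's own trigger. For such a subject the choice is between an event at the full time and censoring at an earlier date. Under one sentence of SAP 7.2 that earlier date is the day of first dose.

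**Working it through.** **Inputs**

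- Missed assessments that trigger censoring: 2 (SAP 5.7)
- Interval assumed in SAP 5.7: 8 weeks = 56 days
- Interval in the protocol and SAP 3.1: 6 weeks = 42 days
- Scan allowance mentioned in SAP 5.7: up to 7 days
- Optional interval after 12 months on treatment: 12 weeks = 84 days
- Dates: original protocol 20 December 2016 and SAP 13 March 2018 (SAP section 1 and page header); all end-of-treatment visits complete by 31 January 2018 (SAP 3.5)

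**1. The plan's own figure.** Window = missed assessments × interval = 2 × 56 = 112 days. This reproduces the SAP exactly, with no visit allowance in it.

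**2. The same rule on the trial's schedule.**

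| Version | Window | Band up to day 112 |
|---|---|---|
| 2 × 42, no allowance | 84 days | 112 − 84 = 28 days |
| 84 + 7, one allowance | 91 days | 112 − 91 = 21 days |
| 2 × (42 + 7), allowance at each scan | 98 days | 112 − 98 = 14 days |

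None of these gives 112, which is 112 / 42 = 2.67 intervals.

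**3. Which events fall in the band.** Count days from the last adequate scan.

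- One scan missed: the subject returns near day 84, and progression found there is counted at 112.
- Two scans missed: the subject returns near day 126 (119 if 7 days early), and progression found there is censored at 112.

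So 112 days sorts on-schedule scans as the trigger intends. The affected events are deaths, and progressions found at an unscheduled or late scan, from the end of the proper window to day 112.

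**4. Illustrative size.** The documents give neither the number of lapsed subjects nor their survival. Assume exponential survival from the last scan with median m. The share of subjects with no further scan who die in the band is exp(−h·w) − exp(−h·112), with h = ln 2 / m and w the proper window.

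| Assumed median | w = 84 | w = 91 | w = 98 |
|---|---|---|---|
| 3 months | 10.1% | 7.4% | 4.8% |
| 6 months | 7.3% | 5.4% | 3.6% |
| 12 months | 4.4% | 3.3% | 2.2% |

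The denominator is subjects with no further scan who are still at risk of a PFS event. It is not all trial subjects.

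**5. The 12-week option.** Two intervals would be 2 × 84 = 168 days, and 112 / 84 = 1.33 intervals, so on paper one missed scan would already lead to censoring. From 20 December 2016 to 31 January 2018 is 407 days, the most follow-up any subject could have by then. After a week-48 scan (day 336), the next 12-week scan is due at day 336 + 84 = 420, and a gap above 112 days needs more than 336 + 112 = 448 days. Both exceed 407. The SAP date itself is day 448, and SAP 3.5 expects no further follow-up.

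**The case against.** The strongest case for leaving the rule alone has four parts.

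**The cut-off works for scheduled scans.** This stands, and it confines the problem to deaths and off-schedule scans. A reader might infer that the rule misclassifies lapsed subjects in general. Step 3 of the working shows that it does not.

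**A flat 84 days would be worse in one respect.** Imaging is only approximately 6-weekly, cycle visits carry a ±3-day window (protocol Table 1-1), and dosing may be delayed by up to 2 weeks (protocol 6.2.3). Progression found on day 86, at the second due scan after only one missed scan, would be censored under a flat 84 days but is counted now. This stands: the replacement needs an allowance, and the 28-day band is the upper end of the range. It does not rescue 112 as a deliberate allowance, because the SAP states its basis and that basis is an 8-week interval.

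**The effect on reporting is small.** SAP section 7 lists efficacy without summarizing it, and SAP 13.3 plans no figures. The tumor assessment, death and subsequent-therapy listings would let a reader re-derive a subject's status. This stands and limits the severity. But the derived PFS and DOR listings (16.2.6.2.6 and 16.2.6.2.7) are the only output for those endpoints, and any later use inherits their flags.

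**The 12-week case has no practical effect.** A reader might infer that the error also runs the other way, with valid events censored after one missed scan on 12-week imaging. The wording would allow that, but the SAP's own dates rule it out.

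**Conclusion.** The 112-day window is wrong for this trial. It is exactly two 8-week intervals, while the protocol and SAP 3.1 specify imaging about every 6 weeks. The proper two-interval window is 84 days, or 91 to 98 with an allowance, so the stated one is 14 to 28 days too long. Deaths and late or unscheduled progressions in that band count as PFS or DOR events when SAP 5.7's own trigger calls for censoring.

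The reach is narrow: individual event or censor flags and times in two listings. A reader might infer that the primary result is biased. The documents do not support that, because ORR, DCR and OS do not use the window and no PFS or DOR estimate is produced. Nor do they show that any subject falls in the band. The percentages in the working rest on assumed exponential survival and assumed medians, and apply to an unknown number of lapsed subjects.

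Severity: should be fixed. The contradiction itself is certain; how many subjects it touches is unknown and may be none.

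**What to change.** 1. In SAP 5.7, replace the 8-week interval with 6 weeks. Set the window to two intervals plus a stated visit allowance, for example 84 + 7 = 91 days, so that progression found at the second due scan after one missed scan still counts. If an allowance is given at each scan, state 98 days.
2. For consistency, define the window by the interval in force, which is 168 days plus the allowance on 12-week imaging, and note that this case cannot arise in the actual follow-up.
3. In SAP 7.2, reconcile the two adjacent sentences on late events. One censors progressions and deaths after the window at the latest adequate assessment; the next censors deaths after the window at the first dose date. If the second is meant only for subjects with no adequate post-baseline assessment, it should say so. This has to be settled together with item 1. Otherwise shortening the window could move a death in the band from an event to censoring on day 1.
4. Re-run the PFS and DOR listings and check any subject whose event falls between the new window and day 112.

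The cost is a few sentences of SAP text, one derivation parameter and a check of two listings. No new data are needed.

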6. STUDY SUBJECT DATA

6.1. Analysis Sets

The Safety Analysis Set (SAF) includes all subjects who received any study treatment. All analyses of safety data will be conducted using the safety set. The SAF is the only analysis set used for all listings and analysis.

6.2. Subject Disposition

Summaries of analysis population membership; final study status (ongoing or discontinuation), including reasons for study discontinuation; treatment status (ongoing or discontinued), including reasons for treatment discontinuation will be produced based on all subjects enrolled in the study. Time on study and duration of treatment will also be summarized.

Screen failures and final subject disposition status will be listed.

6.3. Protocol Deviations

Protocol deviations will be identified and classified as major (violations) before the database is locked. Major protocol deviations may include but are not limited to:

- Violation of Inclusion/Exclusion Criteria
- Dose not properly administered, including
 - Administrations in which protocol required pre-medication were not administered
- Use of prohibited medications

A listing of all protocol deviations will not be provided as part of the study report.

Sponsor: Aduro Biotech, Inc.
Protocol Number: ADU-CL-14
Version and Date: Version 1.0, 13Mar2018

6.4. Demographic and Baseline Characteristics

Subject demographics will be summarized and listed for the SAF. These will include age, sex (Male / Female), ethnicity (Hispanic or Latino / Not Hispanic or Latino), race (American Indian or Alaska Native / Asian / Black or African American / Native Hawaiian or Pacific Islander / White/ Other), baseline height (cm), baseline weight (kg), baseline BMI (kg/m^2), and baseline BSA (m^2). Age will also be categorized as a categorical variable (< 65 , ≥ 65) for reporting.

The following conversions and equations will be used as applicable:

- Height (in cm) = height (in inches) * 2.54
- Weight (in kg) = weight (in lbs) * 0.4536
- BMI (kg/m^2) = weight(kg)/[height(m) 2]
- BSA(m^2) = $\sqrt{[(\text{height(cm)} * \text{weight(kg)})/3600]}$

Duration of time from initial diagnosis to enrollment (in months); cancer type; Siewert classification (where applicable); TNM staging at diagnosis; TNM staging at enrollment; stage at study entry; tumor grade at diagnosis; tumor grade at enrollment; prior systemic therapy, prior radiation and prior surgery (Yes/No); and baseline ECOG will be summarized.

6.5. Medical History

Medical history will be listed.

6.6. Prior and Concomitant Medication

Concomitant medications will be coded to ATC and preferred name based on the WHO Drug Dictionary (WHO-DDE B2, March 2017). Prior medications are those which have been identified to have been discontinued prior to first study treatment (e.g. taken exclusively during the pre-therapy period). Concomitant medications are those which have been identified to have been taken at any point during the on-therapy period.

Prior and concomitant medications will be presented in data listings; medications which do not occur during the on-therapy period will be identified.

Concomitant implants, defined as all implants reported in the eCRF, will be presented in a data listing.

6.7. Anticancer Therapies

Anticancer therapies will be coded to ATC and preferred name based on the WHO Drug Dictionary (WHO-DDE B2, March 2017) and presented in a data listing.

Prior cancer related surgeries and systemic therapies, as well as prior radiotherapy, will be listed.

Sponsor: Aduro Biotech, Inc.
Protocol Number: ADU-CL-14
Version and Date: Version 1.0, 13Mar2018

6.8. Study Drug Exposure

Duration of treatment (in months, as described in 5.3) will be summarized as a continuous variable for CRS-207 and pembrolizumab separately.

The number of infusions of CRS-207 will also be reported as both a continuous and categorical outcome; categories for reporting will be < 5 infusions; 5 to 10 infusions; > 10 to 15 infusions; and > 15 infusions.

The number of cycles of administration (of any dose amount) of pembrolizumab will be reported as a continuous and categorical outcome; categories for reporting will include: < 5 Cycles; 5 to 15 Cycles; > 15 to 25 Cycles; and > 25 Cycles.

The average volume administered for each infusion (or cycle) will be summarized by therapy. This will be calculated for each subject in (mL / infusion or mL / Cycle):
(Sum of Total Volume Administered [mL]) / (Total Number of Administrations)

The average dose intensity for each pembrolizumab cycle will be summarized. This will be calculated for each subject in (mg / Cycle):
(Sum of Total Dose Received [mg]) / (Total Number of Administrations)

The incidence of infusion interruptions and dose reductions, as well as the total number of interruptions and dose reductions, will be displayed by therapy. Reasons for infusion interruptions will be summarized by therapy.

The exposure summary display will be based on the Safety Set.

CRS-207 and pembrolizumab administration, infusion interruption, and dose reduction information, as well as derived drug exposure metrics, will be listed.

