6.3.1 Safety Run-In Period

A Safety Run-in will be completed since there are no precedent data on the use of pembrolizumab with CRS-207. Subjects will be monitored for unacceptable toxicity during the first 28 days (through 7 days after the Cycle 2 dose). During the Safety Run-in, evaluable subjects are defined as those who remain on study for the 28-day monitoring period, subjects with unacceptable toxicity, and subjects who are discontinued for safety reasons at the Investigator's discretion (even if criteria for unacceptable criteria are not met). Treatment of the first 6 subjects that are followed for the 28-day period will be staggered with no more than 1 subject treated per week. In the event that 4 in up to 12 safety-evaluable subjects experience an unacceptable toxicity, the subsequent cohort of 12 subjects enrolled will be administered CRS-207 at a dose reduced by a half-log (dose level -1). In the event of 4 subjects in up to the next 12 safety-evaluable subjects enrolled experience an unacceptable toxicity, the subsequent cohort of 12 subjects enrolled will be administered a reduced dose of CRS-207 (dose level -2). For each dose reduction (to a minimum of 1×10^8 CFU) the first 12 subjects will be treated and unacceptable toxicities assessed as described above. No adjustments will be made to the pembrolizumab dose. The dose levels and dose reduction permutations are provided in Table 6-3.

Table 6-3 Safety Run-in Dose Levels and Dose Reduction Plan

Dose level	Pembrolizumab	CRS-207
1	200 mg	1×10^9 CFU
-1	200 mg	3×10^8 CFU
-2	200 mg	1×10^8 CFU

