6.3.5.1 Pembrolizumab Administration

Pembrolizumab will be diluted and administered as a dose of 200 mg using a 30-minute IV infusion. Sites should target infusion timing to be as close to 30 minutes as possible. However, given the variability of infusion pumps, a window between -5 minutes and +10 minutes is permitted (i.e. infusion time is 30 minutes -5 min/+10 min). Do not co-administer other drugs through the same infusion line. Pembrolizumab infusions will be administered Q3W for up to 24 months. The Pharmacy Manual contains specific instructions for the preparation of the pembrolizumab infusion and administration of infusion solution.

Pembrolizumab Supportive Care Guidelines

Subjects should receive appropriate supportive care measures as deemed necessary by the investigator. Suggested supportive care measures for the management of pembrolizumab-related AEs with potential immunologic etiology along with dose modification guidelines are outlined below. Where appropriate, these guidelines include the use of oral or IV treatment with

corticosteroids as well as additional anti-inflammatory agents if symptoms do not improve with administration of corticosteroids. Several courses of steroid tapering may be necessary as symptoms may worsen when the steroid dose is decreased. For each disorder, attempts should be made to rule out other causes such as metastatic disease or bacterial or viral infection, which might require additional supportive care. The treatment guidelines are intended to be applied when the Investigator determines the events to be related to pembrolizumab.

Note: If the event is determined not to be related to pembrolizumab, the Investigator does not need to follow the treatment guidance (as outlined below). It may be necessary to perform conditional procedures such as bronchoscopy, endoscopy, or skin photography as part of evaluation of the event.

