6.3.5.2 Pembrolizumab Dose Modification and Toxicity Management

Immune-related Adverse Events Associated with Pembrolizumab

AEs associated with pembrolizumab exposure may represent an immunologic etiology. These immune-related AEs (irAEs) may occur shortly after the first dose or several months after the last dose of pembrolizumab treatment and may affect more than one body system simultaneously. Therefore, early recognition and initiation of treatment is critical to reduce complications. Based on existing clinical trial data, most irAEs were reversible and could be managed with interruptions of pembrolizumab, administration of corticosteroids and/or other supportive care. For suspected irAEs, ensure adequate evaluation to confirm etiology or exclude other causes. Additional procedures or tests such as bronchoscopy, endoscopy, skin biopsy may be included as part of the evaluation. Based on the severity of irAEs, withhold or permanently discontinue pembrolizumab and administer corticosteroids.

Dose modification and toxicity management guidelines for irAEs associated with pembrolizumab are provided in [Table 6-4](#). The Medical Monitor will be consulted regarding continued dosing of CRS-207 should any of these events occur. During the Safety Run-in Period withholding pembrolizumab or administering systemic steroids would define an unacceptable toxicity.

Table 6-4 Dose Modification and Toxicity Management Guidelines for Immune-Related Adverse Events Associated with Pembrolizumab

General Instructions:				
Immune-related AEs	Toxicity grade or conditions (CTCAEv4.0)	Action taken to pembrolizumab	irAE management with corticosteroid and/or other therapies	Monitor and follow-up
Pneumonitis	Grade 2	Withhold	
 Administer corticosteroids (initial dose of 1-2mg/kg prednisone or equivalent) followed by taper 	
 Monitor subjects for signs and symptoms of pneumonitis Evaluate subjects with suspected pneumonitis with radiographic imaging and initiate corticosteroid treatment Add prophylactic antibiotics for opportunistic infections
	Grade 3 or 4, or recurrent grade 2	Permanently discontinue		

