6.3.9 Treatment Compliance

Study treatments will be administered by IV infusion by a qualified health care professional at an approved study site. The date, time, and volume of each dose of study drug administered to each subject must be recorded in the dispensing log for the study and the eCRF.

Antibiotics will be provided to subjects following the last dose of CRS-207 as indicated in [Table 1-1](#) or [Table 1-2](#). Site personnel will contact the subject by telephone to facilitate compliance with antibiotic treatment; subjects will be required to record self-administration of antibiotics in a diary.

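### Pembrolizumab dose intensity in SAP 6.8 is really mean dose per administration, so withheld or delayed cycles cannot lower it; CRS-207 exposure has no CFU summary

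*SAP*

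**What the plan says.** SAP 6.8 (Study Drug Exposure) states: "The average dose intensity for each pembrolizumab cycle will be summarized". The unit is mg per cycle and the per-subject formula is ("Sum of Total Dose Received [mg]) / (Total Number of Administrations"). For both drugs, "The average volume administered for each infusion (or cycle) will be summarized by therapy", again with the number of administrations as the divisor. No other averaged amount covers CRS-207, and neither document defines a relative dose intensity.

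The same section also summarizes treatment duration for each drug, pembrolizumab cycles given, CRS-207 infusions given, and counts of infusion interruptions and dose reductions by therapy. Administration data are listed by subject.

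On pembrolizumab dosing, Protocol 6.3.5.1 says "Pembrolizumab will be diluted and administered as a dose of 200 mg using a 30-minute IV infusion" and "Pembrolizumab infusions will be administered Q3W for up to 24 months". The run-in dose-reduction plan in Protocol 6.3.1 adds "No adjustments will be made to the pembrolizumab dose". For immune-related events, Protocol 6.3.5.2 says: "Based on the severity of irAEs, withhold or permanently discontinue pembrolizumab and administer corticosteroids". Table 6-4 offers only continuing, withholding or permanently stopping. Protocol 6.2.3 and 6.3.5.2 also allow delays and non-toxicity interruptions.

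CRS-207 is dosed in CFU, with levels 1×10^9, 3×10^8 and 1×10^8 in Protocol Table 6-3, and Protocol 6.3.4.3 allows individual modification outside the run-in. Protocol 6.3.9 requires recording of "The date, time, and volume of each dose of study drug" given.

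**The concern.** A dose-intensity measure should show how much drug a subject received relative to the schedule. Here the label promises that, but the divisor counts only doses actually given. For a fixed-dose drug whose exposure is lowered mainly by skipping or delaying cycles, the statistic cannot respond to the main way exposure falls.

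Safety and tolerability is the first stated objective, and efficacy is listed but not summarized (SAP 7 and 11), so the safety and exposure tables carry the report. A reader of Table 14.1.4 would see about 200 mg per cycle and could take it as evidence that pembrolizumab was delivered on schedule. The subject-year adjusted event rates in SAP 10.1 add a reason to want the true figure: their denominator runs from first dose to last dose plus 28 days (SAP 5.3), so it includes time spent in gaps between doses.

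For CRS-207 the gap is different. It is the drug with planned lower dose levels, but no summary is expressed in the unit in which it is dosed.

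**Working it through.** The documents state no dose-intensity figure, so there is nothing to reproduce. The check evaluates the SAP formula and compares it with denominators based on schedule or time. Dosing patterns are illustrative assumptions; the 200 mg dose, 21-day cycle and CFU levels come from the protocol.

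**1. Algebra.** With k complete doses, the SAP metric is 200k / k = 200 mg for every k ≥ 1. Withheld cycles cancel out and elapsed time does not enter. Only an incomplete infusion lowers it: one 100 mg infusion among six given yields (5 × 200 + 100) / 6 = 183.3 mg.

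**2. Withheld cycles, six scheduled (assumed).**

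| Withheld | Total mg | SAP metric | mg per scheduled cycle | Relative to 200 mg |
|---|---|---|---|---|
| 0 | 1200 | 200 | 200.0 | 100% |
| 1 | 1000 | 200 | 166.7 | 83.3% |
| 2 | 800 | 200 | 133.3 | 66.7% |
| 3 | 600 | 200 | 100.0 | 50.0% |
| 4 | 400 | 200 | 66.7 | 33.3% |

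**3. Gaps between doses.** Doses at weeks 0, 3, 9 and 15 place the last dose 105 days after the first.
- SAP metric: 800 / 4 = 200 mg.
- Time-based: (105 + 21) / 21 = 6 cycle-equivalents; 800 / 6 = 133.3 mg per 3 weeks; 133.3 / 200 = 67%.

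**4. What the other rows show for that subject.** Cycles given: 4. Duration under SAP 5.3: 105 + 1 = 106 days, against 63 + 1 = 64 days for four doses on schedule. The gap is visible if both values are read for the same subject.

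**5. Limit of a first-to-last-dose denominator.** Take 8 scheduled cycles with 4 withheld, so 800 mg received.
- Final dose at week 21, gaps earlier: (147 + 21) / 21 = 8; 800 / 8 = 100 mg (50%).
- The last four cycles withheld, doses at weeks 0, 3, 6 and 9: (63 + 21) / 21 = 4; 800 / 4 = 200 mg (100%), the same as the SAP.

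A denominator that stops at the last dose therefore misses cycles withheld just before discontinuation.

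**6. CRS-207.** Levels −1 and −2 are 30% and 10% of the starting CFU. A subject with two infusions at 1×10^9 and two at 3×10^8 has a mean of (2 × 10 + 2 × 3) / 4 × 10^8 = 6.5×10^8 CFU, or 65%.
- If the recorded volume is the final infusion volume and is constant (assumption), mean mL does not change.
- If it is undiluted product at 1×10^9 CFU per 1.0 mL (assumption), volumes are 1.0 and 0.3 mL, the mean is 0.65 mL, and mL tracks CFU exactly.

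Protocol 6.3.4.2 leaves preparation to the Pharmacy Manual, and Protocol 6.3.9 does not say which volume is recorded.

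**The case against.** The strongest reply is that the table does not rest on this row. Cycles given, duration per drug, and counts of interruptions and reductions are in the same summary, and each drug has an administration listing (16.2.5.1 and 16.2.5.2). This stands in part. A reader might infer that Table 14.1.4 conceals omitted cycles; it does not, because step 4 shows that gaps can be partly inferred. But two separate distributions do not give each subject's ratio, a count of interrupted infusions is not on its face a count of withheld cycles, and cycles withheld just before stopping shorten the duration and so leave no trace there.

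A second reply is that mL may already follow CFU. This also stands. A reader might infer that average CRS-207 exposure would look unchanged after a ten-fold reduction. That needs a constant infused volume, which the documents neither state nor exclude. What they do establish is that no CFU-based summary is planned. Reductions are counted and listed, although a count does not say which level was received.

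A third reply is that little depends on the row: this is an abbreviated SAP for a synopsis, after development ceased and every subject had completed the end-of-treatment visit (SAP 1 and 3.5), with no significance testing. Dose intensity is not among the safety variables in SAP 2, and the exposure table is one of 15. That limits the importance of the point but does not make the formula measure what its label says.

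**Conclusion.** The pembrolizumab metric is mislabelled and close to uninformative. It is mean dose per administration, equal to 200 mg whenever every infusion is complete, whatever was withheld or delayed. In the worked patterns the shortfall it misses runs from 17% (one of six cycles withheld) to 67% (four of six); these depend on assumed dosing patterns and are not estimates for this trial. The algebra itself rests only on the fixed 200 mg dose.

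For CRS-207, the supported conclusion is that exposure is averaged in mL only and never in CFU. Whether the mL average misleads cannot be settled from the documents.

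The effect is confined to a descriptive exposure table. It would be wrong to infer that any efficacy result, safety count or trial decision changes: nothing in the documents is computed from this metric. The correction is worth making because it is cheap and the present label invites a false reading.

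**What to change.** 1. Rename the current quantity mean dose per administration.
2. Define pembrolizumab dose intensity as total mg received divided by the number of 21-day cycles scheduled from first dose to the recorded discontinuation of pembrolizumab, and relative dose intensity as that value divided by 200 mg. State whether a cycle falling due on the discontinuation date counts. Use a pembrolizumab-specific date, since a subject may continue on CRS-207 alone.
3. If that date is not available per drug, use (last dose − first dose + 21) / 21 as the denominator and say in a footnote that cycles withheld just before discontinuation are not captured.
4. For CRS-207, summarize the assigned CFU level and mean CFU per infusion, adjusted for the fraction infused where recorded. Footnote which volume the mL average refers to.

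The cost is revised SAP wording and a short derivation, mostly from administration data already listed. The fraction infused may not be recoverable, because the protocol does not say that prepared volume is recorded. Reported dose intensity will look less favourable where doses were missed. No dose or clinical rule changes.
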